All participants in the study will be quitting smoking. Risks to all participants will be minimized through frequent monitoring through the web chat portal where participants can chat with study personnel. All participants will be given detailed instructions on how to use either the nicotine replacement therapy, Chantix or bupropion prior to distributing the cessation aids. Finally, all participants will be given a 24 hour monitored telephone number to contact in case of adverse reactions to any of the cessation aids that they are using.

Furthermore, KUMC will be in weekly contact with a clinician or nurse at the Tribal campus health center to review any adverse events or suspected adverse events. We will also be specifically asking participants about adverse events on a weekly basis (via our web –based communication system) and follow-up with phone calls to review anything reported. The following questions will be asked from participants using web-based system to report any adverse events from medications:

- “Have you had any side-effects from your pharmacotherapy this week?”
- “Have you had any urgent or emergent visits to the doctor or a hospital for health problems this week?”

- “Have you had any new unexpected health problems this week that we have not talked about?”

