## **Suicide/Homicide Procedures**

Serious neuropsychiatric symptoms have occurred in patients taking Chantix. These symptoms include changes in behavior, agitation, depressed mood, suicidal ideation, and attempted and completed suicide. While some patients may have experienced these types of symptoms and events as a result of nicotine withdrawal, some patients taking Chantix who experienced serious neuropsychiatric symptoms and events had not yet discontinued smoking. In most cases, neuropsychiatric symptoms developed during Chantix treatment, but in others, symptoms developed following withdrawal of Chantix therapy.

As a result, special caution must be taken if a participant reports an *increase in depressed mood, agitation, changes in behavior not typical for them, or **suicidal thoughts or action** since starting the study medication*. The suicide/homicide protocol will be instituted for all participants noting changes of this sort since starting Chantix.

The suicide/homicide protocol is as follows:

1. Ask participant to describe their symptoms in more detail.

*“Tell me more about what you are experiencing.”*

2. Assess the level of severity.

*“In general, would you say these symptoms are mild, moderate or severe?”*

3. Assess attribution of symptoms to the study medication.

*“Do you believe these symptoms are caused by the study medication or another cause?”*

4. Assess suicide/homicide risk

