### Course of Action

1. If a participant reports **any** suicidal/homicidal ideation, including passive ideation (e.g., thoughts of death, would be better off dead, doesn’t care about living, etc.) or active ideation (has intent to harm, a plan, and means) advise them to stop taking the medication immediately.
2. If the participant is exhibiting active suicidal or homicidal ideation and DOES intend to harm him or herself or someone else:
  - a. Each local mental health center office provides 24 hour a day telephonic crisis response for any citizen in crisis. After discussing the person's problems on the phone the mental health professional (MHP) will decide whether a face to face evaluation is needed.
  - b. Where full time dedicated MHP teams exist, emergency crisis services are available to all persons for both telephone crisis support and face to face evaluations, where clinically indicated, on a 24/7 basis. In offices without dedicated full time crisis teams, clinicians are on call to respond to emergency requests for evaluation and dispositions only for WMMHC clients.
  - c. When a person is judged not to be in an emergency situation, as defined in Montana statute, the person may be given an emergency appointment at the local center for the next day, or referred to a local hospital for voluntary psychiatric admission, or linked with other community resources as appropriate.
  - d. If the individual has a primary therapist, who is not affiliated with the mental health center, that primary therapist will be contacted as soon as practical by the MHP.

- e. Stay with the participant until the crisis worker is able to intervene.
3. If the participant is exhibiting passive suicidal or homicidal ideation and does NOT intend to harm him or herself, the counselor should provide the participant with the **Mental Health Resource Card** and the **Crisis Referral List**. The counselor should also encourage the participant to seek support from friends, family, and possibly mental health resources.
4. If there is no suicide risk but the participant reports neuropsychiatric symptoms (increase in depression, change in mood, agitation, etc.) that are more than mild and that they attribute to the study medication, advise them to stop taking the medication immediately.

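### The suicide/homicide procedure is triggered for Chantix users but not for bupropion users, and no weekly safety question names mood change or thoughts of harm

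*Protocol*

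**What the plan says.** Protocol section III, Risks, states that Chantix and bupropion both carry a boxed warning. People with serious, unusual changes in mood or behaviour, or an urge to hurt themselves or others, should stop the drug.

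The same section fixes three weekly web questions. The first is "Have you had any side-effects from your pharmacotherapy this week". The second asks about urgent or emergent visits. The third is "Have you had any new unexpected health problems this week that we have not talked about". Staff then "follow-up with phone calls to review anything reported".

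Section VI, Suicide/Homicide Procedures, opens with a paragraph about Chantix. It calls for special caution when a participant reports worse mood, agitation, untypical behaviour, or suicidal thoughts or action "since starting the study medication". The next sentence reads: "The suicide/homicide protocol will be instituted for all participants noting changes of this sort since starting Chantix". Step 3 of the procedure is "Assess attribution of symptoms to the study medication". A direct question about thoughts of harm comes at step 4.

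Under Course of Action, item 1 covers passive ideation "or active ideation (has intent to harm, a plan, and means) advise them to stop taking the medication immediately". Item 4 deals with symptoms without suicide risk. It advises stopping only for those "that are more than mild and that they attribute to the study medication".

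In section IV, the Chantix exclusions list a suicide attempt, suicidal thoughts and thoughts of harming others in the past 12 months. The Zyban exclusions list none of these.

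**The concern.** Two things do not fit together. First, the Protocol recognises the same warning for two drugs but institutes the procedure for changes after starting only one of them. Staff who follow that sentence literally could leave a bupropion user outside it.

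Second, the procedure waits for a report, yet the fixed weekly questions do not ask about the symptoms that should be reported. A participant who does not regard low mood or thoughts of harm as a drug side-effect or a health problem can truthfully answer no to all three. The drug may then continue when item 1 of Course of Action would have stopped it. The event may also be absent from the adverse events that section VI says are reported at study completion.

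**Working it through.** No arithmetic beyond counting applies, and the Protocol states no figure to reproduce. The relevant places are set side by side.

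**1. The weekly questions against the trigger (section III, Risks; section VI)**

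| Weekly question | Names mood, behaviour or harm? | Needs attribution to the drug? | Needs a medical visit? |
|---|---|---|---|
| Side-effects | No | Yes | No |
| Urgent or emergent visit | No | No | Yes |
| New unexpected health problem | No | No | No |

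So 0 of 3 name the trigger symptoms. Only the third (1 of 3) is open to ideation that the participant does not blame on the drug and that led to no visit. It works only if the participant sees such thoughts as a health problem.

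**2. Whether attribution should matter at this stage**

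For symptoms without suicide risk, item 4 makes attribution part of the stop rule, so the first weekly question suits that rule. For any ideation, item 1 applies whatever the cause. Step 3 already has staff ask about attribution after a report. The weekly screen therefore does not need to ask it first.

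**3. The two drugs under the boxed warning**

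| | Chantix | Bupropion |
|---|---|---|
| Boxed warning acknowledged (section III) | Yes | Yes |
| Suicidality or harm exclusions, past 12 months (section IV) | Yes | None listed |
| Named in the sentence instituting the procedure (section VI) | Yes | No |

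A person barred from Chantix because of recent suicidal thoughts is not barred from bupropion by the Zyban list. Bupropion is the drug that the trigger sentence omits.

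**4. The mood measures (section V, Measures)**

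The CES-D-10, PANAS negative affect and Minnesota withdrawal scale are scheduled at weeks 1, 3, 5, 7 and 12 and at month 6. That is 5 of weeks 1 to 12, leaving 12 − 5 = 7 weeks without them (2, 4, 6, 8, 9, 10 and 11). Weeks 8 to 11 are four such weeks in a row. For weeks 9 to 11 the session plan lists only one individual email per week, while pharmacotherapy runs to week 12. No score or answer on these scales is linked to the procedure.

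**5. The other channels (sections III and VI)**

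These are the side-effect prompt before each session, the 24-hour line, web chat, clinic contact, physician monitoring, the automatic inquiry after a medical encounter, and third-party reports of serious events. Each can bring a problem to light. None is stated to ask about mood or thoughts of harm.

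**The case against.** The case on the other side has real weight. The third weekly question is open and needs neither attribution nor a visit. Anything reported gets a call, and many other channels exist. The scales in section V do ask about mood. Recent suicidality is screened out for Chantix. Participants are promised detailed instructions before cessation aids are distributed, and the consent pages and medical screeners are not shown, so what participants are told to report cannot be judged.

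This stands as mitigation and rules out any claim that mood goes unasked. It does not close the gap: the scales are not weekly and lead to no action, and the Chantix screen has no counterpart for bupropion.

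A reader might infer that section VI gives two contradictory scopes, the study medication and Chantix. The text does not compel that. The section opens with Chantix alone, so the broader phrase may simply mean Chantix there. On either reading, the sentence that institutes the procedure omits bupropion, and that is the firm defect.

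A reader might also infer that bupropion users have no stop rule at all. They do: item 1 of Course of Action covers any participant reporting ideation, and item 4 refers to the study medication generally. What they lack is a mention in the sentence that starts the procedure.

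**Conclusion.** The point holds in a limited form. Of the two drugs that the Protocol places under the boxed warning, one is missing from the sentence that starts the procedure. None of the three fixed weekly questions names the symptoms on which the procedure depends. Detection is partly mitigated but incomplete.

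The Protocol gives no event rate, so the number of missed events cannot be estimated, and the documents do not show that any event will be missed. The conclusion rests on staff following the wording as written, and on the screeners and consent text, which are not shown, being left out of account.

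A reader might infer a threat to the comparison of arms. The documents do not support that: both arms are offered the same drugs, and the primary abstinence analysis is not affected. This is a safety-ascertainment point that should be corrected because the possible harm is serious and the change is small.

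**What to change.** 1. **Section VI, Suicide/Homicide Procedures.** In the sentence that institutes the procedure, replace Chantix with Chantix or bupropion. Leave the wider study-medication wording in the preceding sentence, so that nobody now covered is removed.
2. **Section III, Risks.** Add one weekly web item that does not ask for a cause, in two parts: (a) worse depressed mood, agitation or untypical behaviour this week; (b) any thoughts of harm to oneself or to another person this week.
3. **Handling of answers.** State that a yes to (b) starts the procedure for any participant, whatever product they use and also if they use none. The study offers five products as well as no pharmacotherapy, so tying (b) to two drugs would leave someone on NRT or no drug with only a routine call. A yes to (a) gets the phone follow-up already planned. For a Chantix or bupropion user, that call moves to the section VI steps if it confirms a change of the kind described there.

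The attribution step and the stop rules stay as written.

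The cost is more than one extra question. Everyone in the study is quitting, and section VI itself says that some of these symptoms may come from nicotine withdrawal, so there will be extra alerts. Staff must read answers promptly. Each time the procedure starts, Course of Action item 5 requires a detailed case note and immediate contact with two physicians, after the crisis worker has intervened if the participant is actively suicidal. Sending part (a) through the phone call first keeps mild withdrawal symptoms from starting the full procedure automatically.

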participants in our tobacco cessation studies. We are comfortable with individual's self-report, mostly because we have done this successfully for years in our other tobacco cessation studies.. For Participants at a Tribal college: Participants who choose to take Chantix will also be monitored by Tribal clinic, will correspond with [name] about participants taking Chantix. All Participants will be prompted to discuss any side effects prior to starting each web-session and will be given the study office phone number (24-hour coverage) to contact study staff and/or the investigators to report adverse events. On – the - ground physician will decide if they need to directly communicate with participants when participants initiate or while they are taking medications. Our staff will also have weekly contact with participants (via our web-based communication system). [name] will provide secondary review and communicate with the on-the-ground physician or participant if need clarification on any screener responses, if the participant reports side-effects from study medications, if the participant has an Adverse Event (AE) that could be due to study or study medication related, or if the participant requests to speak with a study physician. We will follow the NIH guidelines for reporting adverse events to the Human Subjects Committee. Any problems needing medical attention will be referred to [name] (consulting physician) and the patient's personal physician. The study medication will be discontinued in patients who become pregnant, report use of any other medications that contain bupropion (e.g., Wellbutrin), or develop a contraindication. Patients will be instructed not to smoke cigarettes during treatment. Women of child bearing age who are participating in the program and requesting to use Chantix or Zyban will agree to use a form of birth control during the course of the study.

Alternatives to participating in the study are to quit cold turkey, use other smoking cessation programs, purchase nicotine gum or patches from the pharmacy, obtain a prescription for bupropion or other smoking cessation products from their physician, or continue to smoke. Other risks for participating in the study are minimal and include those associated with the inconvenience of completion of several questionnaires, email follow-up assessments, and the inconvenience of logging onto the internet for web-based counseling sessions.

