**Participant Incentives:** Incentives will be identified by focus group participants, CAB members, and Native research team members. For ANBL, we have used things like quit kits (hard candy, toothpicks, etc.), stress balls, flute music CD’s for relaxation, and Rez-robics® (aerobic dance videos that include pow wow and traditional dance), among other things. We will provide participants with gift cards for participating in the research. At baseline, we will give participants \$20 gift cards for survey participation. At 12-weeks and 6-months, we will give participants \$40 gift cards for survey participation. We will also give participants a \$10 gift card for providing saliva for cotinine analysis at the time points above. In addition to the above incentives, participants will also receive a \$10 gift card if they complete at least 5 of the weekly web sessions. If the participants complete all 8 weekly web sessions they will receive a \$20 gift certificate. All participants will be asked to provide saliva at baseline, 12-weeks, and 6-months. We ask for repeat samples from all participants for two reasons: (1) nicotine metabolism of smoking has not been previously examined and we plan to look at decreases in use, as well as quitting; and (2) we do not want some participants to be able to obtain additional incentives because we do not want to bias our results. We do not anticipate a problem with participants’ willingness to provide saliva; our ANBL programs have a 100% participation rate in this, even though it is voluntary for participants to provide saliva.

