### Phase 3: Data Analysis and Dissemination

The objectives of this phase are 1) to conduct data analysis and 2) to disseminate the program.

In Year 5, we will complete post-intervention assessments, data analyses and report writing.

Process and outcome data will be presented at scientific conferences and manuscripts will be submitted to peer-reviewed scientific journals. Ultimately, we envision that **I-ANBL**, if efficacious, could be disseminated and

used as a culturally tailored smoking cessation intervention that could be adopted across different tribal colleges.

**Sample Size and Power:** The primary endpoint will be cotinine verified 7-day point prevalence abstinence at Month 6. Per preliminary findings, we expect a 30% cessation rate in the **I-ANBL** arm and a 15% cessation rate in the **I-FV** arm. Using the chi-square test, and the assumptions above, 121 participants in each group will give us 80% power to detect this difference with a type I error rate of 5%.

Given retention rates from our earlier studies, we expect attrition rates to be approximately 20% over the 6 month study period. Therefore, we anticipate needing to enroll 300 participants at baseline in order to have 242 active participants at 6 months.

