Furthermore, KUMC will be specifically asking participants weekly about potential adverse events (via our web-based communication system). Any report of an urgent/emergent or unexpected medical encounter by a study participant would automatically trigger an inquiry by our study personnel to find out what happened, create an AE report and forward that to [name] and the on-the-ground physician to review and decide whether the AE was study or study medication related and whether participant should be taken off pharmacotherapy or should be advised to stop participating in the study.

Because the anticipated level of risk involved with all possible pharmacotherapy use is low, adverse events will be recorded and reported at the completion of the study along with other study results. In addition, serious adverse events will be monitored and handled as described below:

Definition: Consistent with the definition by the FDA, a serious adverse event includes any event experienced by a study subject while on the study medication that:

- Is fatal
- Is life-threatening (subject was at risk of death from the event as it occurred)
- Is disabling or incapacitating
- Requires inpatient hospitalization or prolongs a current hospitalization
- Is a congenital anomaly in the offspring of a subject who received the study medication
- Required intervention to prevent permanent impairment or damage

Monitoring: Information about serious adverse events experienced by study subjects will be monitored by the following means:

- Report given by study subjects to study staff either in person or by telephone
- Report given to study staff by study subjects' family or friends either in person or by telephone
- Report by the subject's physician or other health care provider involved in their care
- Report from a hospital or other healthcare facility where the study subject(s) is being treated for the serious adverse event
- Other persons that may have knowledge of such serious adverse event.

Procedure: Upon receiving report of a serious adverse event:

- The study staff will page [name] (at beeper [name]) as soon as possible
- The study staff will give the necessary information to [name]
- [name] will obtain other necessary information and complete the "MED WATCH" form for each serious adverse event
- [name] will make a decision whether to stop the study medication temporarily or permanently and inform study staff of this decision

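### The three fixed weekly adverse-event questions look back one week only, with no catch-up after an unanswered week, so some urgent visits and new health problems are never asked about

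*Protocol*

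**What the plan says.** Protocol Section III (Risks) says participants will be asked about adverse events weekly through the web-based communication system, and it prints the wording. The first question concerns side effects of the pharmacotherapy. The second is "Have you had any urgent or emergent visits to the doctor or a hospital for health problems this week" and the third is "Have you had any new unexpected health problems this week that we have not talked about". All three carry the same one-week limit. Follow-up phone calls are promised for whatever has been reported.

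Other routes for learning of events are also described:

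- Section III: "All Participants will be prompted to discuss any side effects prior to starting each web-session". No look-back limit is given.
- Section III: a 24-hour telephone line, and weekly contact between the study centre and the campus health center to go over known or suspected adverse events.
- Section III: "Participants who choose to take Chantix will also be monitored by Tribal clinic". Section VI adds that the primary care physician monitors varenicline use.
- Section VI (reporting of adverse events): "Any report of an urgent/emergent or unexpected medical encounter by a study participant would automatically trigger an inquiry". Serious events may also be reported by treating providers, hospitals, family, friends or others.
- Section VI (Suicide/Homicide Procedures): this protocol is triggered by mood or behaviour changes "since starting the study medication", a cumulative window.

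On missed sessions, Section V (Participant Incentives) pays a gift card to participants "if they complete at least 5 of the weekly web sessions", and a larger one for all 8.

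**The concern.** A participant who answers nothing in week 4 and returns in week 5 is asked only about week 5. If an emergency visit took place in week 4, the correct answer to the question as printed is no. Nothing then prompts the participant to mention it, and the inquiry in Section VI cannot start because it needs a report.

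The stake is completeness of safety capture. Adverse events are to be recorded and reported with the study results, and the 24-hour clock for serious events runs from when the study physician learns of them. Both depend on the event reaching the study. This matters mainly for participants who take a medication; the protocol does not say how many will. Section III notes a boxed warning for both prescription drugs and a 1 in 1000 seizure risk with bupropion at 300 mg/day.

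Because the protocol itself fixes the question wording, this is not a detail left to a later document.

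**Working it through.** There is no stated figure to reproduce. The check is a reading of the text plus a count of weeks.

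**1. What the wording covers.** Suppose a participant answers in week k, gives no answer for the next m weeks, and answers again in week k+m+1.

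- Current wording: weeks k and k+m+1 are asked about; the m weeks between are not.
- Wording based on the last answer: the second answer covers m+1 weeks, so none stays open.
- With m = 0, both wordings cover the same single week.

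The closing words of the third question exclude problems already discussed. They narrow the question and do not lengthen its window.

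**2. Whether another route closes the gap.**

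| Route | Reaches back past the week? | Asks every participant about urgent visits or new problems? |
|---|---|---|
| Side-effect prompt before sessions | No limit stated | No; side effects only |
| Follow-up phone calls | Not stated | No; only what was reported |
| 24-hour line | Yes, if used | No; the participant must call |
| Weekly review with campus clinic | Not stated | No; limited to what the clinic knows |
| Varenicline monitoring | Not stated | No; varenicline users only |
| Third-party serious-event reports | Yes | No; serious events only, and someone must report |
| Suicide/homicide protocol | Yes, since starting medication | No; mood and behaviour changes only |

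What remains is an urgent visit or new problem in an unanswered week that the participant does not see as a side effect and does not call about, that the clinic does not know of, and that either is not serious or is not passed on by anyone.

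**3. Size.** The inputs are 8 weekly sessions and an incentive threshold of 5 (Section V, Participant Incentives).

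- Sessions missed by someone exactly at the threshold: 8 − 5 = 3, and 3/8 = 37.5% of session weeks.
- This carries over to the questions only under three assumptions: they are answered only in weeks when a session is done, a missed session is not made up later, and the participant stops at exactly 5. The protocol states none of these.
- Under the first two assumptions, anyone at or above the threshold has between 0 of 8 weeks (all sessions done) and 3 of 8 weeks not asked about.
- With the revised wording, the same person has 0 weeks open after answering at session 8 or at any later point. At most 3 stay open, if the last three sessions are missed and no answer follows.

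**4. Who the fix cannot reach.** Section V (Sample Size and Power) enrols 300 "in order to have 242 active participants at 6 months": 242/300 = 80.7% retained, and 300 − 242 = 58 (19.3%) not. For any retained participant who answers the revised questions at month 6, no week stays open. For a participant who has left for good, the weeks after the last answer stay open. These are retention figures for the power calculation, not response rates to the safety questions.

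**The case against.** The strongest reply is that the protocol has several overlapping safety routes and that little slips past all of them. Much of this stands. The weekly clinic contact is scheduled, active review and does not depend on the participant logging in. Inpatient hospitalization on study medication meets the serious-event definition, so the gravest visits have third-party routes. The untimed side-effect prompt appears to apply at week 12 and month 6 as well, since both are internet sessions. These points narrow the gap, but none of the routes asks each participant about urgent visits or new problems in the missed time.

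A second reply is that short weekly recall is a reasonable choice and a longer window is less precise. This does not defend the present wording: for anyone who answers every week the two windows are identical, and the longer one applies only where nothing would otherwise be asked.

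Two stronger readings are tempting, and the documents support neither:

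- **That 37.5% of the safety follow-up is lost.** The 5-of-8 figure is a payment tier, not an expected response pattern. The protocol describes the weekly web contact separately from the session prompt and never says that missing a session means missing the questions.
- **That adverse-event counts will be biased between arms**, because Hypothesis 2 predicts higher adherence with I-ANBL. This needs the same unstated tie to log-in, and the Statistical Analyses section plans no between-arm test of adverse events.

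**Conclusion.** The point holds in a narrow form. The printed questions do not ask about an unanswered week, and no section says how that week is recovered. An event there that the participant does not take for a side effect reaches the study only through a call, the clinic's own knowledge, or a third-party report of a serious event.

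The size cannot be stated, since the protocol gives neither a weekly response rate nor a link between the questions and session log-in. Three of 8 weeks is an illustration under the assumptions in the working, not an estimate, and no number of missed events is claimed. Nor does the text support saying that such events are simply lost.

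The primary endpoint is unaffected. The change is worth making because the gap is foreseeable, it concerns safety capture, and closing most of it costs little.

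**What to change.** In Section III (Risks):

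- In all three questions, replace the one-week limit with *since you last answered these questions*, or *since starting the study* for someone who has never answered.
- Ask for the approximate date of any event reported. This also limits double counting.
- Put the same three questions at the existing week 12 and month 6 sessions. The participant flow shows no session or assessment between those two points, so they are the natural places to catch up. At month 6, word the first question to include effects after stopping a medication, because Section VI notes that symptoms can follow varenicline withdrawal.

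The cumulative window in the suicide/homicide procedures shows that this kind of look-back already fits the protocol.

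The cost is three reworded web items, one date field and their placement in two sessions that already exist, with no new visit or staff. Recall after a gap is less precise than weekly recall, and participants who never answer again are not recovered.
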